Clinical Protocol 2018-008

Effect of TrueTear use on anterior corneal surface imaging quality

PRINCIPAL INVESTIGATOR: [name] MD

CO-INVESTIGATORS: [name]; [name], OD; [name], OD; [name], OD

Price Vision Group &
Cornea Research Foundation of America
[name]
[name]

PURPOSE OF THE STUDY:

To evaluate the utility of TrueTear™ to improve anterior corneal surface imaging quality before cataract surgery, refractive lens exchange, or laser refractive surgery.

BACKGROUND:

Consistent and accurate mapping of the ocular surface is required to perform accurate preoperative calculations for a variety of “refractive” surgeries including cataract surgery, refractive lens exchange, and laser refractive surgery. Accurate mapping of the anterior surface of the eye is needed in order to obtain “keratometry” readings with a topographer (Tomey) and an optical biometer (LensStar™) to determine the appropriate intraocular lens power to implant in association with cataract surgery or refractive lens exchange. Likewise with new topography-directed laser refractive treatments using Contoura™ mapping of the cornea, it is essential that the mapping reflect the accurate contour of the ocular surface and not distortions caused by dry spots on the surface. If the imaging includes surface irregularities caused by dry spots, then the excimer laser treatment would transfer these irregularities onto the cornea, permanently distorting the optical system of the eye and causing poorer vision rather than improved vision.

The importance of a normal tear film for accurate corneal surface imaging has long been recognized,^{1,2} and becomes particularly apparent when patients have dry eyes and/or low ambient humidity stresses patients’ ocular surfaces causing the three imaging systems noted above to produce unusable images. During imaging, the eye may be open for a longer than normal interval between blinks, and the drier the ambient air or the more stressed the ocular surface is from underlying disease, the more distorted these images can become. Using artificial tears, humidifiers, or having patients sit with their eyes closed for 20 to 30 minutes does not reliably improve the test results.

Because the TrueTear™ system uniquely improves all three layers of the tear film, we hypothesize that use of this device could be beneficial for obtaining more accurate imaging when the imaging is negatively impacted by the quality of the ocular surface.^{3,4}

STUDY SPONSOR: Cornea Research Foundation of America
[name]

STUDY DESIGN:

This is a single-center cohort study.

CHARACTERISTICS OF THE RESEARCH POPULATION:**NUMBER OF SUBJECTS:**

50 subjects scheduled to undergo cataract surgery or refractive lens exchange and 50 subjects scheduled to undergo laser refractive surgery will be enrolled for a total of 100 subjects.

GENDER OF SUBJECTS:

Males and females will be enrolled.

AGE OF SUBJECTS:

Age 18 years and older will be enrolled because that is typically the minimum age for these surgeries.

RACIAL AND ETHNIC ORIGIN:

Subjects can be of any racial and ethnic origin.

INCLUSION CRITERIA:

- Male or female of any racial or ethnic origin, age 18 years or older
- Able to provide written, informed consent
- Scheduled to undergo routine imaging for cataract surgery, refractive lens exchange, or laser refractive surgery

EXCLUSION CRITERIA:

- A cardiac pacemaker, implanted or wearable defibrillator, or other implanted metallic or electronic device (e.g. cochlear implant) in the head or neck
- Chronic or frequent nosebleeds, a bleeding disorder (e.g. hemophilia), or another condition that can lead to increased bleeding
- A known hypersensitivity (allergy) to the hydrogel material that comes into contact with the inside of the nose during use of the TrueTearTM device
- Pregnancy
- Presence of any ocular disease or condition which in the investigator's opinion would confound the study results

VULNERABLE SUBJECTS:

Most study subjects will be new patients, but it's possible that a few long-term patients might be interested in enrolling. To minimize coercion, the study consent clearly states that participation is voluntary and the decision whether to participate or not will not affect the patient's care.

METHODS AND PROCEDURES:

SCREENING: Prospective subjects who are scheduled to undergo imaging for cataract surgery, refractive lens exchange, or laser refractive surgery will be considered for enrollment into the study. Medical and ophthalmic histories will be recorded.

ENROLLMENT: Subjects who meet the inclusion and exclusion criteria will be informed about the opportunity to participate in the study. Subjects will be entered into the study after providing written informed consent. Each subject will be instructed that if they decide to participate, they may withdraw at any time.

EXAMINATION: Subjects are expected to complete the study in one visit.

Table 1. Visit Schedule	Visit 1
Informed Consent	X
Inclusion/Exclusion	X
Medical & Ophthalmic History	X
SPEED (dry eye symptom) Questionnaire	X
Ophthalmic Examination	X
Anterior corneal surface imaging	X
Use TrueTear™ device	X
Repeat anterior corneal surface imaging	X
Adverse Events	X

IMAGING:

- All subjects will have 3 images taken of the anterior corneal surface with the Tomey topographer.
- Cataract surgery and refractive lens exchange patients will have 5 LensStar™ images taken.
- Laser refractive surgery patients will have 10 Contoura™ images taken.
- The imaging will be done before and after use of the TrueTear™ device.

STUDY TREATMENT: Subjects will be carefully instructed regarding proper use of the TrueTear™ device. The device will be utilized for 3 sequential 1-minute cycles at the intensity level selected by the patient to provide a gentle tingling sensation.

PRECAUTIONS FOR MINIMIZING POTENTIAL RISKS

The study will use an FDA-approved device. Subjects assigned to TrueTear™ will be carefully instructed in proper use. The instructions for use note that the most frequently reported adverse events ($\geq 2\%$ incidence) were nasal pain, discomfort or burning, transient electrical discomfort, nosebleed, nasal congestion, headache, trace blood in nostril, and facial pain.

Subjects will be instructed to let the investigator or study coordinator know immediately if they notice any problems or discomfort. Any study subject who experiences an adverse event will receive appropriate treatment and be allowed to immediately withdraw from the study.

SAMPLE AND DATA ANALYSIS:

The primary outcome measure will be the change in the ocular surface asymmetry index (SAI) after use of the TrueTear™ device. The null hypothesis is that the mean SAI will not change significantly after TrueTear™ use. The research hypothesis is that SAI will decrease significantly after TrueTear™ use. The hypothesis will be assessed using a one-sided paired t-test at a significance level of 0.05. Secondary outcome measures will include the change in the surface regularity index (SRI) measured with corneal topography and the variances of the keratometry readings obtained with the topographer, Lenstar, and Contoura imaging devices. The study participants will be scored on baseline signs and symptoms of ocular dryness and associations between the outcome measures and ocular dryness scores will be assessed.

This is a first-of-its-kind study. Considering the range of patients who undergo each type of surgery, we anticipate that enrollment of 50 subjects per treatment arm in each surgical cohort will provide adequate statistical power to detect clinically meaningful differences.

REFERENCES:

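### The dryness associations are planned with no surgical-cohort term, so for outcomes measured in both cohorts a pooled analysis can create or hide a relation if the cohorts differ in both dryness and outcome

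*Combined protocol and SAP*

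**What the plan says.** Under Number of Subjects, "50 subjects scheduled to undergo cataract surgery or refractive lens exchange and 50 subjects scheduled to undergo laser refractive surgery will be enrolled", making 100 in all. The cohort sizes are therefore set by design.

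Under Sample and Data Analysis, the plan states: "The study participants will be scored on baseline signs and symptoms of ocular dryness". On how those scores are then used, it says only that "associations between the outcome measures and ocular dryness scores will be assessed". No model, test, significance level, covariate or stratification is given for these associations. The primary test is specified: "The hypothesis will be assessed using a one-sided paired t-test at a significance level of 0.05". It has no cohort term either. The only wording in that section that refers to the cohorts is the sample-size statement that "enrollment of 50 subjects per treatment arm in each surgical cohort will provide adequate statistical power".

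Under Imaging, "All subjects will have 3 images taken of the anterior corneal surface with the Tomey topographer", so SAI, SRI and topographer keratometry exist in both cohorts. The other devices do not overlap: "Cataract surgery and refractive lens exchange patients will have 5 LensStar™ images taken", and Contoura images are taken only in the laser cohort.

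**The concern.** Cataract or lens-exchange patients and laser refractive patients may differ in baseline dryness. They may also differ in how their topography changes after the device, for reasons unrelated to dryness. A correlation across all 100 subjects then contains two things: the relation among patients of the same kind, which is the one of interest, and the contrast between the two cohort means. With a 50:50 split fixed by quota, the size of the second part is partly a product of the design.

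The Background proposes that the device helps when a poor ocular surface degrades the imaging. It says that "the drier the ambient air or the more stressed the ocular surface is from underlying disease, the more distorted these images can become". Enrolment does not require a dry eye, so the dryness association is the only planned analysis that addresses this idea directly. A pooled result could support the idea because two surgical groups differ, or miss a relation that is present in both.

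**Working it through.** **The plan's own figure.** The 50 per cohort cannot be reproduced, because no effect size, SD or power value is given. For orientation, 80% power needs a standardized paired change of 0.36 with 50 subjects or 0.25 with 100 (one-sided 0.05). It needs a correlation of 0.39 with 50 or 0.28 with 100 (two-sided 0.05).

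**Inputs.** From the documents: two cohorts of 50. Assumed, because the documents are silent: a two-sided 0.05 test of correlation; normal data; cohort differences dx in dryness score and dy in improvement (for example, fall in SAI), in within-cohort SDs; and a within-cohort correlation r_w.

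**Formula.** For two equal cohorts, the pooled correlation is

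r_pooled = (r_w + dx·dy/4) / √[(1 + dx²/4)(1 + dy²/4)].

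**Creating an association (r_w = 0, dx = dy).**
- 0.3 SD: 0.0225/1.0225 = 0.02
- 0.5 SD: 0.0625/1.0625 = 0.06
- 0.8 SD: 0.16/1.16 = 0.14
- 1.0 SD: 0.25/1.25 = 0.20

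In 40,000 simulated trials per scenario, the pooled test rejected in 5.9%, 9.2%, 28% and 53% respectively. With a cohort term it rejected in 4.8% to 5.1%. If only one of the two variables differs, even by 1 SD, dx·dy = 0, the pooled correlation is zero and rejection stays at 5%.

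**Hiding an association (r_w = 0.30, dy = −dx).**
- 0.5 SD: (0.30 − 0.0625)/1.0625 = 0.22; pooled power 61%
- 0.8 SD: (0.30 − 0.16)/1.16 = 0.12; pooled power 21%
- 1.0 SD: (0.30 − 0.25)/1.25 = 0.04; pooled rejection about 5%

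With a cohort term, power is 86% in all three.

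**When the cohort term costs something (r_w = 0.30, dy = 0.30·dx).** Here the cohort difference in improvement is entirely due to dryness, so the between-cohort contrast is real signal. At dryness differences of 0.5, 0.8 and 1.0 SD, pooled power is about 88%, 91% and 93%, against 86% with the term.

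**Primary mean SAI change.** If the cohort mean changes differ by d within-cohort SDs, the plain paired t-test counts that difference as error. Its standard error is inflated by √(1 + d²/4), which is 1.03, 1.08 and 1.12 at d = 0.5, 0.8 and 1.0. For a true mean change of 0.25 SD (one-sided 0.05), simulated power is about 78%, 76% and 74%, against about 80% using within-cohort error. At d = 0 the two tests are equivalent.

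**The case against.** The strongest reply is that the documents do not state that the cohorts are pooled. A reader might infer that a pooled analysis is prescribed, but the phrase about the study participants says who is scored and does not define an analysis set. The sample-size sentence speaks of each surgical cohort, which would fit a within-cohort analysis. This stands: pooling is the natural reading, not a stated rule. The text still permits a pooled analysis, and leaves the choice open until the data have been seen.

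A reader might also infer that any difference between the cohorts produces a false association. It does not. Both dryness and outcome must differ, the effect is negligible at 0.3 SD on each, and the large figures need 0.8 to 1.0 SD on each. No figure in the documents supports differences of that size.

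Nor does the problem reach every outcome. LensStar and Contoura variances each exist in one cohort only, so their associations are already within-cohort.

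Two further extensions are tempting but unsupported. One is that different numbers of images per cohort drive different SAI changes: the order of devices is not given, and SAI comes from the topographer images that every subject has. The other is that noise rising with dryness invalidates the test: no test is named for the associations, and the Background says images become more distorted, not that the pre-to-post change becomes more variable.

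Finally, the association is not the primary outcome and carries no success criterion, and the cohort term is not entirely free. Both points stand and limit the weight of the finding.

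**Conclusion.** The point holds for SAI, SRI and topographer keratometry variance. With two fixed quotas and no cohort term, the natural pooled analysis can be confounded by surgical cohort. The size depends wholly on assumed cohort differences. False positives range from about 6% at 0.3 SD on both variables to 53% at 1.0 SD. Power for a correlation of 0.30 ranges from 61% at opposing differences of 0.5 SD to almost nothing beyond the 5% test level at 1.0 SD. The gain for the primary test is smaller, about 2 to 6 percentage points of power under the assumptions shown. The unstratified primary test is not invalid; it is only somewhat conservative when the cohorts differ. This is a cheap improvement to a supporting analysis, not a flaw in the trial's main conclusion.

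**What to change.** State in the analysis section that:

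- associations between topographer outcomes (SAI, SRI, keratometry variance) and dryness scores will be estimated with a surgical-cohort term, or by a rank correlation stratified by cohort, with the two cohort-specific estimates shown;
- LensStar and Contoura associations will be analysed within the one cohort in which each is measured;
- the primary mean SAI change will be the equally weighted average of the two cohort means, tested with within-cohort error, with each cohort's mean change and confidence interval reported.

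If both quotas fill, the primary point estimate is unchanged and only its standard error differs. Cohort is known for every subject, so no data, visits or subjects are added. The cost is one degree of freedom and, if a cohort difference in change is entirely due to dryness, a loss of about 2 to 7 points of power for the association (86% against 88% to 93%).
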